5.1 Primary endpoint - Tolerability

- The grade of any adverse events (AE) requiring medical intervention within three months of treatment should be low. Device-based treatment will be considered tolerable if less than 30% of participants treated have an "Overall AE Score" larger than Grade 2 AE at the 3month follow-up (visit 4) as assessed via Common Terminology Criteria for Adverse Events (CTCAE), U.S. Department of health and human services, Ver 5.0, Nov 27, 2017.
- The rate and nature of spontaneous healing of the treated cNF lesion and any safety related event including potential wound formation and wound healing should be equivalent to expectations from alternative method(s). Safety evaluation includes rating of treatment associated sequele by end of study, e.g. dyspigmentation and scarring and overall investigator rating compared to expectations.

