6.5.6 Participant enrollment and handling

Every effort will be made to arrange routine clinical follow-up for all participants, independent of how many study-associated visits they have completed.

Enrolment into study will take place at the two participating hospital departments (Department of Dermatology, Bispebjerg University Hospital and Department of Dermatology and Venereology, Sahlgrenska University Hospital).

The total duration of the study from enrolment of first participant to end of data collection is expected to be 1.5 years.

Expected total duration of each participants' participation is 9 months, with milestone evaluation after every 3 months.

In total 20 participants will be enrolled (target enrolment is 10 participants at Department of Dermatology, Bispebjerg University Hospital and 10 participants at Department of Dermatology and Venereology, Sahlgrenska University Hospital). Enrolment is not stratified. Limits can be changed based on the coordinating investigators discretion if recruitment to one study group turns out being not possible or according to experience unrealistic. Enrolment is based on participants remitted to the centers for diagnosis and treatment of NF1. Participants with urgent treatment need are not enrolled.

Participants of the study continue their course and normal registration in the hospital department. Each study visit is registered and documented in the hospital file parallel to registrations in the case reports of the study.

Histology taken at the Swedish center will be labeled using the study codes which do not contain the personal identification number of the study person. The samples will be used only for research purpose and not for patients care and treatment. The samples will be analyzed separately by a pathologist and the PI in Sweden. After the analyses the samples will be stored in Biobank Väst in Sahlgrenska Universitetssjukhuset,

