Investigator overall scoring of treatment side effect severity (one X)									
Absent / Normal Mild Moderate Severe Life-threatening or disabling Death									
Grade 0	Grade 1	Grade 2	Grade 3	Grade 4	Grade 5				

Fig 7. The primary end-point of the study is the investigator's grading of adverse effects following treatment as measured directly after treatment and in all subsequent patient follow-up visits.

According to the defined endpoint, the minimum number of patients must therefore be calculated to support a sufficiently high power for the statement that not more than 30% of patients will experience an overall side-effect of Grade 3 or above based on Common Terminology Criteria for Adverse Events (CTCAE), U.S. Department of health and human services, Ver 5.0, Nov 27, 2017.

Secondary endpoints regarding efficacy, feasibility etc. are also measured and analyzed throughout the study, and form important data for analysis, but are not included in the calculation of the minimum number of patients.

To obtain an initial indication of the necessary number of participants needed in the study, a simple estimation based on the conventional calculation of sample size to estimate a proportion or apparent prevalence with specified precision can be used.

A simple binary outcome is considered:

- Accept: Participants have Grade 2 side effects or lower
- Reject: Participants have Grade 3 side effects or higher

Based on substantial previous clinical experience with the study device (used for other skin treatments), severe side effects and adverse events are very rare, and an estimated proportion of 90% having Grade 2 or lower side-effects is therefore a reasonable starting point for the calculation (P=0.90).

As the measurement of side-effects by the investigator is subjective and with a quite course resolution, a total error can be set to 30% (e = ± 0.15), roughly reflecting the interval between the six possible gradings. A standard confidence interval of 95% can be used (Z = 1.96).

At these inputs, the minimum population for the investigation can be calculated as follows:

$$N = (Z^2 \times P \times (1 - P))/e^2 = (1.96^2 \times 0.90 \times (1 - 0.90)/0.15^2) = 15.37$$

At 16 participants in the study, it is therefore possible to say with 95% confidence that the results of treatments will fall within the acceptable group. The minimum number of participants at various other proportions is shown in Table 2.

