Table 2. Calculated minimum population in an investigation for obtaining statistical significance at a cure rate of p and with a error of $\pm 15\%$

р	0,95	0,90	0,85	0,80	0,75	0,70	0,65	0,60	0,55	0,50
Ν	9	16	22	28	33	36	39	41	43	43

In a second step, power curves can be calculated against an alternative base-line of equal proportions having acceptable and rejectable grades of side-effects (the null hypothesis).

Fig 8. shows the power curve for the study containing the above minimum 16 participants as a function of the actual obtained passed AE-profiles. At the hypothesis of 90% having an acceptable AE-profile after HIFU treatment the power is calculated to be 71%.

Similarly, curves correlating the number of necessary participants at fixed power-levels of 80% and 90% at the hypothesized 90% having an acceptable AE-profile after HIFU treatment can be calculated. As shown in Fig. 9, the study will require 20 participants if a power of 80% is needed, while 26 participants will be needed to reach a power of 90%.

[figure not shown]

Fig. 8. Power curve showing the probability of being able to detect difference between HIFU treatment with 90% passed AE profile against a baseline treatment with 50% acceptable proportion. At the projected succes rate of 90%, the difference in cure rate can be detected with a 95% confidence level and power of above 71% if the population in the investigation is 16 participants.

[figure not shown]

Fig. 9. Power curves showing the necessary population to obtain power levels of 80% and 90%. At the projected acceptable AE-profile of 90%, the hypothesis can be confirmed with a power of 80% probability if the population is 20 participants and a poer of 90% if the population in the investigation is 26 participants.

In conclusion, the statistical analysis shows that participation as low as 16 patients will give an acceptable power, provided the AE profile is in the expected range. At worse AE-profiles, or requirements for a higher power-level in comparison with alternatives, the required population size naturally increases, and populations above 20 will typically needed.

In consideration of the status as an initial tolerability and feasibility study performed on a relatively young population group with low expected drop-out, it is considered that a total of **20 participants distributed among the two centers** will be a well-balanced population taking ethical, clinical and practical issues into due consideration.

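### The plan claims 95% confidence, but no calculation in it addresses the 30% tolerability limit: at n = 20 the section 5.1 rule passes a device with a true 30% Grade 3+ rate 41.6% of the time

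*Combined protocol and SAP*

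**What the plan says.** Section 5.1 gives the numerical success criterion for the primary endpoint: "Device-based treatment will be considered tolerable if less than 30% of participants treated" have an overall adverse event score above Grade 2 at the three-month visit. No interval, test or error rate is attached.

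Section 7 returns to the same endpoint in order to size the study. It dichotomises the score ("Reject: Participants have Grade 3 side effects or higher"), words the statement to be supported as "not more than 30" per cent, and assumes "an estimated proportion of 90% having Grade 2 or lower side-effects". It sets the precision at ±0.15 with Z = 1.96 and obtains 15.37, rounded up to 16. For 16 participants it then concludes that "it is therefore possible to say with 95% confidence that the results of treatments will fall within the acceptable group".

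A second step in section 7 computes power against a null of equal acceptable and unacceptable proportions. It gives 71% power at 16 participants, 80% at 20 and 90% at 26, and concludes that "participation as low as 16 patients will give an acceptable power". Section 6.5.6 fixes the planned size: "In total 20 participants will be enrolled".

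**The concern.** A reader of section 7 will take it that a tolerable verdict carries 95% confidence that the Grade 3+ rate is acceptable, meaning below 30%. The section 5.1 rule gives no such assurance. It passes any observed proportion under 30%, however wide the uncertainty, and with about 20 participants that uncertainty is large.

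This is the only numerical success criterion for the primary endpoint, and it informs whether larger studies should follow. If the final report repeats the 95% sentence beside a result such as 4/20 or 5/20, it will claim more than the data can show. The small difference in how sections 5.1 and 7 word the limit also leaves one attainable result, 6/20, without an agreed verdict.

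**Working it through.** **Inputs.** n = 20 (section 6.5.6); minimum n = 16, assumed Grade 3+ rate 1 − 0.90 = 0.10, e = 0.15 and Z = 1.96 (section 7); limit 30% (section 5.1).

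**1. The precision figure.** N = Z²P(1−P)/e² = 1.96² × 0.90 × 0.10 / 0.15² = 15.37, so 16. This reproduces the plan. The formula gives the half-width of an interval around an estimate of 90%. The 30% limit does not enter it.

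**2. The power figures.** They reproduce from the formula for two independent proportions (pooled variance, two-sided 5%, n per group), although the study has one group:

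Power = Φ[(0.4√n − 1.96√(2 × 0.7 × 0.3)) / √(0.9 × 0.1 + 0.5 × 0.5)]

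- n = 16: (1.600 − 1.270)/0.583 = 0.566, power 71.4%.
- n = 20: power 81.3%, and 20 is the smallest n reaching 80%.
- n = 26: power 90.7%, and 26 is the smallest n reaching 90%.

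The baseline is 50% acceptable. A 30% limit on Grade 3+ corresponds to 70% acceptable, which appears nowhere in the calculation.

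**3. What the section 5.1 rule does.** At n = 20, below 30% means at most 5 events (6/20 is exactly 30%). At n = 16 it means at most 4 (4/16 = 25%, 5/16 = 31.25%). The pass probability is P(X ≤ c) with X binomial(n, p). At n = 20 and p = 0.30, the terms for 0 to 5 events are 0.0008 + 0.0068 + 0.0278 + 0.0716 + 0.1304 + 0.1789 = 0.416.

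| True Grade 3+ rate | n = 20, at most 5 | n = 16, at most 4 |
|---|---|---|
| 10% | 98.9% | 98.3% |
| 20% | 80.4% | 79.8% |
| 30% | 41.6% | 45.0% |
| 35% | 24.5% | 28.9% |
| 40% | 12.6% | 16.7% |
| 50% | 2.1% | 3.8% |

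**4. What a passing result shows.** For 5/20 the exact two-sided 95% (Clopper-Pearson) interval is 8.7% to 49.1%, and the one-sided 95% upper bound is 45.6%. For 4/16 the one-sided bound is 48.4%.

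**5. What 95% confidence about 30% would need.** The one-sided 95% exact upper bound is 28.3% at 2/20 and 34.4% at 3/20, so at most 2 events are allowed. P(X ≤ 2 | 20, 0.30) = 0.0355, a type I error of 3.5%. P(X ≤ 2 | 20, 0.10) = 0.677. At n = 16 only 1 event is allowed (bound 26.4%), with a pass probability of 51.5% at a true 10%.

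**6. The two wordings.** Below 30% and at most 30% can differ only when 30% of n is a whole number. At n = 20 that is exactly 6 events. The probability of this is 0.9976 − 0.9887 = 0.9% at a true 10% and 0.608 − 0.416 = 19.2% at a true 30%. At n = 16 the wordings coincide.

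**The case against.** The study calls itself an initial tolerance study, and a point-estimate go/no-go is a defensible choice at that stage. Any such rule passes roughly half the time when the truth sits on the limit. At the planned 10% rate this one passes 98.9% of the time. That stands: the rule itself may be kept. It does not justify attaching 95% confidence to the rule.

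It can also be said that the precision formula does imply something about 30%, since an observed 10% plus 15 points is 25%. But this holds only if the observed rate is near 10%, whereas the rule passes anything below 30%. At 16 participants even 2 events (12.5%) would not bring the exact one-sided bound under 30%.

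Three stronger readings are tempting, and the documents do not support them.

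- *Two competing decision rules, with a false-pass rate of up to 61%.* Section 7 is sizing text that refers back to the defined endpoint; only section 5.1 states a rule. Under the inclusive wording a true 30% is acceptable by definition, so 60.8% is only the limiting false-pass rate just above 30%.
- *The trial's only formal decision.* Section 6.5.5 has numerical termination criteria, including a cure rate below 20% at three months. Section 16 suspends the study for device-related serious events, and section 5.1 has a second tolerability criterion on healing.
- *The rule must become at most 2 of 20.* That is a trade-off. A device performing as planned would then pass 67.7% of the time instead of 98.9%, and 80% would need 28 participants.

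**Conclusion.** The point holds in a limited form. The 95% confidence statement in section 7 is wrong as written, because no calculation in the plan tests or bounds the Grade 3+ rate against 30%. The section 5.1 rule, taken alone, passes a true 30% rate 41.6% of the time and a true 40% rate 12.6% at n = 20. What a bare pass at 5/20 supports, with exact limits, is a true rate below about 49%. The difference in wording is a minor inconsistency confined, at the planned size, to 6/20.

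These figures assume independent participants, one binary score each, and 20 (or 16) analysed. The analysed number could differ, since section 6.5.6 lets enrolment limits change and section 6.5.4 replaces and does not analyse withdrawals before three months. The 30% limit itself is taken as given.

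**What to change.** 1. Use the section 5.1 wording (less than 30%) in section 7 as well.
2. Delete the 95% confidence sentence, or correct it to say that 16 participants give an approximate 95% interval of ±15 points if 90% have an acceptable score.
3. Report the Grade 3+ proportion with its exact (Clopper-Pearson) 95% interval, and state the rule's pass probabilities at n = 20: 98.9% at a true 10%, 41.6% at 30% and 12.6% at 40%.
4. State that the 71%, 80% and 90% power figures refer to a 50% baseline and not to the 30% limit.
5. If the sponsor wants to claim 95% confidence that the true rate is below 30%, rest the claim on the one-sided 95% exact upper bound being below 30% at the number actually analysed. At n = 20 that means at most 2 events, with type I error 3.5% and pass probability 67.7% at a true 10%. A fixed count should not be carried to another n: at n = 18 only 1 event would be allowed.

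Items 1 to 4 are edits to section 7 and the reporting plan and need no extra patients. The cost is that the stated confidence becomes less favourable. The edits should be made before outcome data are seen, because the study is open-label and section 6.6 allows interim analysis from three months at the investigator's decision.

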6.5.3 Criteria and procedures for participant withdrawal or lost to follow up

- Exclusion criteria identical to non-inclusion criteria, however, appearing during the study.
- Patients acquiring disease of higher priority contraindicating their further participation or making participation not possible in practice.
- Patients' decision to leave the trial, irrespective of reason.
- Patients' non-adherence to the study schedule.
- Unforeseen hazards or significant clinical adverse events making continuation of the study not ethical.

6.5.4 Withdrawal from the Study

Each participant has the right to withdraw from the study at any time without prejudice. The investigator may discontinue any participant's participation for any reason, including failure to comply with the protocol (as judged by the investigator such as compliance below 80%, failure to maintain appointments, etc.).

Should a participant withdraw from the study, the reason(s) must be stated on the case report form, and a final evaluation of the participant should be performed.

Patients who go off treatment must be followed for AEs for at least 30 days from treatment or biopsy.

Reason for withdrawal from study is documented in the case report form. Withdrawals after HIFU treatment and before the 3-month visit are replaced and not included in the analysis of results (but registered as dropouts). Withdrawals after 3 months are replaced on investigators discretion.

6.5.5 Study Termination Criteria

The study may be terminated for multiple potential reasons. Some of these reasons include:

• Majority of participants experience severe and unbearable pain, on investigator's decision based on a minimum of 3 participants.

- Unbearable immediate wheal and flare reaction with severe itch and swelling and urticaria disseminating to larger skin areas experienced by a minimum 3 patients, on investigator's decision as indicated above.
- Any systematic (general or local) acute response to the treatment deemed by the investigator to be a clinically significantly different clinical or psychological reaction or adverse event than expected.
- The efficacy of the treatment is in the majority of participants at the 3-month interim assessment (visit 4) deemed to be unacceptably poor by the investigator or the sponsor. Unacceptable efficacy is defined as cure rate below 20% at the 3-month visit, based on a sample of minimum 8 participants in each group of the study.

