Clinical recording of the study includes clinical assessment of healing and therapeutic effect on the tumors. Such assessment follows clinical criteria described in textbooks, guidelines and clinical consensus in the specialty of dermatology. Prior to study, the two investigator sites have coordinated their clinical assessment method.

The chosen 9-month total study period is considered acceptable for observation of tolerance and curative effect of HIFU for cNF with observation of primary therapeutic effect after 3 months. Assessments includes monitoring of the wound healing phase, observation of late recurrences, and observation of scarring.

The study includes no follow up medication, but the study can involve use of wound healing dressings and other remedies in the wound healing phase on investigators individual recommendation. The study involves no standard recommendation on post treatment care, which is anticipated to be simple.

After the study participants are followed in the respective hospital departments according to their needs and the department routines.

Participants who drop out of the study before the 3-month visit voluntarily or for non-medical reasons, including non-adherence, will be replaced by new participant(s). Withdrawals after 3 months are replaced on investigators discretion with considerations to the impact of the overall investigation schedule.

Patient with incomplete cure documented by ultrasound imaging assessment or biopsy and histology after 3 months or subsequent control visit (indicated by clinical suspicion of reoccurrence) will be offered a second treatment based on the standard treatment offered by the center. The specific treatment will be decided by the investigator and the patient based on the extent and severity of the recurrence.

The study will conclude when all participants have completed the 9-month study period, when all data are on file, and the statistical analysis is concluded. Interim analysis of data collected after 3 months and later is allowed, per investigator's decision.

If the study design is deemed inferior, the protocol can be amended.

The study produces no physical test samples relevant for purposes outside the study.

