6.7 Monitoring plan

The study will be monitored separately in the two centers. In Denmark, it is intended that the study is monitored by GCP-enheden ved Københavns Universitetshospital. In Sweden, the study is intended to be monitored by Gothia Forum for Clinical Studies. Both are units serving the respective regional healthcare researchers.

As the monitoring unit in the region of the sponsor's center, the Danish GCP unit will have the responsibility to coordinate a shared monitoring plan, where each party monitors the investigation center. The monitoring plan will be made with due consideration to the centers designated tasks and reflect considerations to specific risks in the tasks performed.

An overview of monitoring activities and focus-areas are given in Table 4.

Investigation activity	Stage / Visit	GCP Unit KU, DK	Gothia Forum, SE
Monitoring plan	Before	Х	(x)
Initiation of study	Before	Х	Х
Recruitment	Before	Х	Х
Screening and inclusion/exclusion	Visit 1	Х	Х
Selection and documentation of lesions for treatment	Visit 2	Х	Х
HIFU Treatment	Visit 2	Х	Х
Post treatment documentation and evaluation by investigator and patient	Visit 2	Х	Х
Follow-up visits with documentation and evaluation by investigator and patient	Visit 3 - 6	Х	Х
Ultrasound scanning – Procedure and analysis from measurements	Visit 2 – 6	Х	
Biopsies – Procedure and analysis from pathological report	Visit 2 – 4		Х
CRF entry and REDcap	Visit 1 - 6	Х	Х
Statistical analysis	After		Х
Study Reporting	After	х	
Close of study – Archive readiness	After	Х	Х

lable 4. Monitoring	activities in the two	o monitorina unite	s used by the	e investigation centers.

7 Statistical design and analysis

The number of patients recruited for participation in the study will be balanced with due consideration to ethical aspects and the statistical background for conclusive statements regarding the primary endpoint.

As mentioned above, the primary endpoint of the study is to document the tolerability and safety profile of the treatment. As the main measurable endpoint, the grade of overall adverse effects following treatment is best suited for evaluation of participants in the study. The measurement of this endpoint is done subjectively by the investigator according to a conventional grading system, and is measured directly after treatment and at all subsequent control visits. The input template for measurement is illustrated in Fig. 7.

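### Sections 5.1 and 7 leave open how visits combine into the tolerability verdict, and Section 6.5.4 drops treated participants who withdraw before month 3

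*Combined protocol and SAP*

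**What the plan says.** **Aim and rule.** The first bullet of Section 5.1 states the aim: the grade of any AE "requiring medical intervention within three months of treatment should be low". The next sentence gives the rule. Treatment "will be considered tolerable if less than 30% of participants treated have an" unacceptable result. A participant's result is unacceptable when the overall AE score is "larger than Grade 2 AE at the 3month follow-up (visit 4". Table 1 places visit 4 at 12 ± 2 weeks.

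**Section 7.** The text says that the overall grade "is measured directly after treatment and at all subsequent control visits". The Fig. 7 caption describes the primary endpoint as the investigator's "grading of adverse effects following treatment as measured directly after treatment and in all subsequent patient follow-up visits". Section 7 then restates the 30% criterion for Grade 3 or above as the basis for the sample size. It names no visit there, and it allows exactly 30%, whereas 5.1 requires a figure below 30%. Neither section says whether a participant's value is the worst, the last or a cumulative score.

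**Withdrawals.** Section 6.5.4 says: "Withdrawals after HIFU treatment and before the 3-month visit are replaced and not included in the analysis of results". It makes no distinction by reason. It also says that patients who go off treatment "must be followed for AEs for at least 30 days from treatment or biopsy". Section 6.6 states a narrower replacement rule, for "Participants who drop out of the study before the 3-month visit voluntarily or for non-medical reasons", with non-adherence included.

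**The concern.** The aim covers a period, while the rule names one visit at the end of it. Section 4 expects harms that come early: instant pain, wheals that fade in 20-30 minutes, and wound-healing complications such as infection. Section 14.4 adds an unexpectedly strong burn with delayed healing. Some of these could be over by week 12. The documents do not say how often any would reach Grade 3.

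If the score describes the participant's state at visit 4, a Grade 3+ event seen at visit 2 or 3 and since resolved is absent from the numerical verdict. Section 6.5.4 opens a second route: a treated participant who has a Grade 3+ event and then leaves is removed from both numerator and denominator, and a replacement is enrolled.

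The study is open-label and the investigator does the grading. An unstated combining rule could therefore be settled after the results are known.

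**Working it through.** **Inputs.** N = 20 (Sections 6.5.6 and 7). Planned Grade 3+ rate 10%, the complement of the 90% acceptable proportion in Section 7. Limit 30% (Sections 5.1 and 7). The documents give neither the fraction of Grade 3+ participants resolved by visit 4 (r) nor the fraction who withdraw before it (w). Both are assumptions, shown as ranges. The 15% rate is an assumed intermediate value.

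**The plan's own figure.** 1.96² × 0.90 × 0.10 / 0.15² = 15.37, rounded up to 16, as in Section 7. This reproduces and is not in dispute; it is the source of the 10% rate.

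**Cut-off.** 5/20 = 25% passes under either wording. 6/20 = 30% fails under 5.1 and passes under Section 7. P(X = 6) for Bin(20, p) is 0.9% at p = 0.10 and 19.2% at p = 0.30. The rest uses 5.1's wording, a pass at 5 or fewer.

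**Worst grade through visit 4.** P(X ≤ 5) is 98.9% at p = 0.10 and 41.6% at p = 0.30.

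**Visit window.** On the literal reading, the rate counted at visit 4 is p(1 − r). The verdicts differ when worst grade fails (k ≥ 6) and at most 5 of those k are still Grade 3+ at visit 4:

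Σ over k ≥ 6 of Bin(k; 20, p) × P(Bin(k, 1 − r) ≤ 5)

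| r (assumed) | p = 10% | p = 15% | p = 30% |
|---|---|---|---|
| 0% | 0% | 0% | 0% |
| 10% | 0.5% | 2.4% | 11.9% |
| 25% | 0.9% | 4.8% | 29.9% |
| 50% | 1.1% | 6.5% | 51.6% |
| 80% | 1.1% | 6.7% | 58.3% |

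Check at p = 0.30, r = 0.50: the visit-4 rule passes 93.3% of trials, worst grade passes 41.6%, and the difference is 51.6% before rounding. If the visit-4 score is cumulative, every entry is 0%.

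**Withdrawals, with worst grade used.** Assume that a fraction w of Grade 3+ participants withdraws, that nobody else does, and that each is replaced until 20 complete. The completer rate is p(1 − w)/(1 − pw), and the number of withdrawals W is negative binomial (20, 1 − pw). The excluded analysis passes if X ≤ 5 of 20. The all-treated analysis passes if (X + W)/(20 + W) < 0.30.

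| w (assumed), p = 30% | Excluded passes | All treated passes | Verdicts differ |
|---|---|---|---|
| 10% | 50.2% | 47.2% | 3.0% |
| 25% | 64.4% | 49.9% | 14.5% |
| 50% | 87.4% | 51.4% | 36.0% |

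At p = 10% the verdicts differ in 0.05%, 0.2% and 0.3% of trials. The all-treated pass rate exceeds 41.6% because the denominator grows: 6/21 = 28.6% passes where 6/20 does not.

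**Example.** Take 5 Grade 3+ among 20 completers, plus 2 Grade 3+ participants who withdrew. Excluded: 5/20 = 25%, a pass. All treated: 7/22 = 31.8%, a fail.

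**The case against.** A cumulative reading is possible. The sentence before the rule sets a three-month window, the score is called overall, and Section 7 speaks of patients experiencing Grade 3 or above without naming a visit. On that reading the visit-window problem vanishes. This stands as a possibility. Against it, the score is repeated at every visit, no combining rule is given, and the CRF, which might state a recall period, is not among the documents.

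Early events are also not lost to the trial. The secondary safety endpoints (Section 5.2) record them immediately after treatment and at all follow-up visits. The second bullet of 5.1 covers any safety-related event, including wound healing, and is not tied to visit 4. Section 16 suspends the study for device-related SAEs. All of this stands, but none of it enters the 30% count, and the second bullet has no threshold.

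The large percentages need a rate of 30%, three times the planning value and exactly at the limit, where the worst-grade rule itself passes 42% of trials. The withdrawal model is harsh: treatment is a single session, Section 7 expects low drop-out, and only Grade 3+ participants are assumed to leave. These limits on the size stand. They do not resolve the conflict between 6.5.4, 6.6 and the denominator in 5.1. The 30-day AE follow-up records an event without returning the participant to the analysis.

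**Conclusion.** The point holds as an unresolved conflict of wording. Sections 5.1 and 7 give two versions of the 30% criterion with no combining rule and different cut-offs. Section 6.5.4 excludes treated participants whom 5.1 counts. Followed as written, these rules can remove an early Grade 3+ event from the numerical verdict.

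A reader might infer that the rule certainly misses early events, or that such events escape the trial's safety assessment altogether. The documents support neither: a cumulative visit-4 score is not excluded, Section 7's version carries no visit restriction, and the other safety provisions still apply.

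The effect is small at the planned 10% rate (at most 1.1% and 0.3% of trials) and modest at 15% (2.4% to 6.7% for the visit window). It becomes large near the limit: about 12%, 30% and 52% for the visit window and 3%, 15% and 36% for withdrawals, at assumed fractions of 10%, 25% and 50%. Confidence is high that the sections conflict and that 6.5.4 excludes treated participants. It is moderate that the verdict would actually be biased. This should be fixed before data are seen.

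**What to change.** In 5.1, Section 7 and Fig. 7:

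- Define the primary variable as each treated participant's maximum overall CTCAE v5.0 grade from HIFU treatment through visit 4, taken from the post-treatment visit 2 score, the visit 3 and 4 scores, and the AE records. Grade 3 or above is a failure.
- Use all treated participants as the denominator, including those who withdraw and are replaced, each with the highest recorded grade. Add a sensitivity analysis that counts withdrawals without a Grade 3+ record as failures.
- Reconcile 6.5.4 and 6.6 with this analysis set.
- Use one cut-off wording, expressed as a proportion of all treated.
- Keep the visit-4 score as a secondary measure of persisting AEs. If persisting harm is what the primary endpoint is meant to capture, reword the aim to say so and report worst grade beside it.
- Before data are seen, state whether the aim's condition about medical intervention limits which AEs count. State also whether expected session pain and wheal-and-flare, which have their own secondary endpoints, enter the maximum grade. Otherwise expected transient reactions could drive the result.

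**Cost.** No new visit or assessment is needed: Table 1 already schedules AE reporting and medical-team scoring at visits 2, 3 and 4. The failure count can only stay equal or rise, the denominator may exceed 20, and withdrawn participants may have only 30 days of AE data. The 90% planning value names no window and should be confirmed for this one.
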